### **Operating Characteristics for Stopping Rule (PL=0.10)**

Clinical Scenario	Early Stopping Probability	Achieved Sample Size (25th, 50th, 75th percentile)
Response rate is 0.1	0.79	10, 17, 37
Response rate is 0.2	0.24	40, 40, 40
Response rate is 0.3	0.044	40, 40, 40

Reference:

Thall, Peter F., Simon, R. and Estey, E.H. "Bayesian sequential monitoring designs for single-arm clinical trials with multiple outcomes," Statistics in Medicine 14:357-379, 1995.

**11.1** In an update of the data on October 6, 2010, 12 of the first 21 patients treated (57%) had achieved CR or Cri. This was achieved with minimal drug related side effects, and allowed several patients to proceed safely to allogeneic stem cell transplant. These data are very encouraging and if consistent in a larger number of patients may show that single agent CMC-544 therapy is superior to standard combination intensive chemotherapy with regard to safety and efficacy. We therefore propose to increase the total number of patients treated to 60 patients to allow a more accurate assessment of the response rate and to define more precisely predictive

factors for response and outcome with CMC-544 therapy. The analysis of predictive factors for response, durability of response, and survival will be conducted using standard statistical methods, and will be descriptive, for the purpose of guiding future large scale and pivotal trials with CMC-544 in ALL.

**11.2** Following the update of January 7, 2011, it is proposed to treat 20 patients with a weekly schedule of CMC-544, to gain experience with efficacy and toxicity. This portion of the study should protect against an overall response rate < 40%. Therefore the study will stop early if the number of responses over number evaluable is: 0/7, 1/10, 2/14, and 3/17. Otherwise a total of 20 patients will be treated. The response and toxicity evaluations will be descriptive.

**11.3** Following an update on December 2, 2011, the weekly schedule was assessed to demonstrate equal or better efficacy and perhaps less toxicity than the single dose every 3-4 weeks. In the first 15 evaluable patients, 8 (53%) achieved marrow CR. An additional 20 patients will be treated for a total of 40 patients to assess more precisely the response and toxicity rates with the weekly schedule.

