#### **2.4      Update of October 6, 2010**

At present, a total of 21 patients with refractory relapse ALL have been treated. Fifteen of them were in second salvage or worse; eight of them have translocation 4;11 or Philadelphia positive ALL. Overall, 12 of 21 patients have achieved either CR (n=5) or Cri (n=7), for an overall response rate of 57%. This is even better than what is expected using standard combination intensive chemotherapy in first salvage, with which the CR rate would be expected to be about 30%. Toxicity has been minimal. There were two episodes of tumor lysis responding to standard measures. Fever on Day 2 post therapy is common. Transient grade 1-3 elevations of liver enzymes have been observed, which are expected and self-limited. Two patients died within four weeks, one of them with progressive disease. Overall the treatment appears to be extremely effective with minimal toxicity. This has allowed so far at least 4 patients to undergo allogeneic stem cell transplant. Based on the findings we propose to 1) allow treatment of patients in first salvage regardless of the duration of first CR, and 2) increase the total number of

patients to 60 to allow more accurate assessment of the overall response rate and define more precisely predictive factors for response to therapy.

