## **2.6 Update of December 2, 2011**

This study has completed accrual of 20 patients on the weekly schedule. The early analysis shows encouraging results with trends for similar or better efficacy and less

toxicity. Among the first 15 evaluable patients, 2 achieved CR (12%), 5 achieved CRp (31%) and 1 achieved CRi (6%). Thus, 8 of 15 evaluable patients (53%) achieved marrow CR. Five of the 7 evaluable responders (71%) achieved MRD negativity. Three patients underwent allogeneic SCT; no VODs were noted. Transient liver enzyme elevations grade 1-2 were noted in 5 of 20 (25%), severe in 2.

In discussions with Pfizer, we emphasized the importance of these findings but the limited number of patients makes definite conclusions difficult. It was agreed to increase the number of treated patients on the weekly schedule by another 20, for a total of 40 patients, to assess more precisely the response and toxicity profile compared with the 49 patients treated with the single dose every 3-4 weeks.

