## **11.0 Statistical Considerations**

A total of up to 60 patients will be treated. The primary endpoint for efficacy is response which is defined as CR, CRI or PR.

The method of Thall [1995] will be employed to perform interim futility monitoring.

The trial will be stopped early if:  $\Pr[\theta > 0.20 | \text{data}] < 0.10$ . Where  $\theta$  denotes the response rate. That is, given the outcomes from the patients who have already been evaluated, if we determine that there is less than a 10% chance that the response rate is 20% or more, we will stop the trial for futility. We assume a prior distribution of  $\theta \sim \text{beta}(1,1)$ . Stopping boundaries corresponding to this probability criterion are to terminate the trial if:

(# patients with CR, CRi, or PR) / (# patients evaluated)

≤ 0/10, 1/17, 2/24, 3/31, 4/37

The operating characteristics for the futility monitoring rule are shown in the following table.

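### Both cohorts were enlarged after encouraging looks with no pre-set extension rule, so the pooled response rate leans upward given extension and should be shown beside rates by stage

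*Combined protocol and SAP*

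**What the plan says.** Section 11.0 sets the endpoint: "The primary endpoint for efficacy is response which is defined as CR, CRI or PR". Its only interim rule is for futility: "The method of Thall [1995] will be employed to perform interim futility monitoring", with stopping boundaries "0/10, 1/17, 2/24, 3/31, 4/37". The operating-characteristics table tops out at 40 patients, which I take to be the maximum before the first enlargement.

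**Single-dose cohort.** Section 11.1 reports that "12 of the first 21 patients treated (57%) had achieved CR or Cri", calls this very encouraging, and continues: "We therefore propose to increase the total number of patients treated to 60 patients". The stated aims are a more accurate response rate and better-defined predictive factors. Section 2.4 widened eligibility in the same step: "Based on the findings we propose to 1) allow treatment of patients in first salvage", whatever the length of the first remission. By the December 2011 update (section 2.6) this cohort numbered 49.

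**Weekly cohort.** Section 11.2 set 20 patients, with futility stops at 0/7, 1/10, 2/14 and 3/17, and called the evaluation descriptive. Section 2.6 then says: "The early analysis shows encouraging results with trends for similar or better efficacy". At that point 20 patients had been accrued and 8 of 15 evaluable patients had a marrow CR. Section 2.6 adds that the numbers were too small for firm conclusions. Section 11.3 follows: "An additional 20 patients will be treated for a total of 40 patients to assess more precisely the response and toxicity rates". Section 2.6 sets these 40 against the 49 single-dose patients.

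The plan gives no rule for extending a cohort, no reporting by stage and no adjusted estimate.

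**The concern.** Each extension followed a look at the response rate, and the rate was part of the stated reason. Among trials that would have been extended for that reason, the patients counted at the look are on average a favourable sample. Counting them in the final rate carries part of that favour forward.

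Section 11.1 asks whether the early result will hold in more patients. A rate that includes the early patients partly confirms itself, so only patients outside the look can answer that question. The results are also meant to guide later pivotal trials, and section 2.4 sets them against an expected CR rate of about 30% with standard first-salvage chemotherapy. A reader who takes the pooled figure as the early figure with extra precision would expect somewhat too much of the next trial.

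**Working it through.** **1. The plan's own figures.** With a beta(1,1) prior the posterior is beta(1+x, 1+n−x), and the rule stops when Pr(θ > 0.20) < 0.10. For 0/10 this is 0.8^11 = 0.086; for 0/9 it is 0.8^10 = 0.107, so 10 is the first stopping point. The other four boundaries reproduce in the same way. An exact recursion to 40 patients gives stopping probabilities of 0.783, 0.240 and 0.045 at response rates 0.1, 0.2 and 0.3, against the plan's 0.79, 0.24 and 0.044. The futility rule is as described, and it says nothing about when to extend.

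**2. Inputs.** Looks: n1 = 15 (weekly) and n1 = 21 (single-dose). Final sizes: N = 40 (section 11.3), and N = 49 (section 2.6) or 60 (section 11.1). The trigger c (extend if X1 ≥ c) and the true rate p are assumptions, shown as ranges. The counts at the looks are CR/CRi or marrow CR and are treated here as the responses.

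**3. Formula.** With X1 ~ Bin(n1, p), and later patients unaffected by the look:

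excess of the pooled rate given extension = (E[X1 | X1 ≥ c] − n1·p) / N.

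Example, weekly, c = 8, p = 0.40: E[X1 | X1 ≥ 8] = 8.659, so (8.659 − 6)/40 = +6.6 points. At p = 0.50: (9.071 − 7.5)/40 = +3.9.

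| Cohort | Assumed trigger | p = 40% | p = 50% |
|---|---|---|---|
| Weekly, N = 40 | passing the section 11.2 futility rule | +0.7 | +0.2 |
| Weekly, N = 40 | 6/15 | +3.1 | +1.3 |
| Weekly, N = 40 | 7/15 | +4.8 | +2.5 |
| Weekly, N = 40 | 8/15 | +6.6 | +3.9 |
| Single-dose, N = 49 | 7/21 | +1.6 | +0.4 |
| Single-dose, N = 49 | 9/21 | +3.9 | +1.6 |
| Single-dose, N = 49 | 12/21 | +8.6 | +5.2 |
| Single-dose, N = 60 | 12/21 | +7.0 | +4.2 |

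The futility row conditions on clearing all four section 11.2 boundaries within 20 patients. At p = 60% the 8/15 excess falls to +1.8. For scale, the standard error of a rate from 40 patients is about 7.8 points.

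**4. Effect of enlarging.** The numerator in step 3 is fixed by the look, so a larger N shrinks the excess. With c = 8/15 it is +13.3 (p = 40%) and +7.9 (p = 50%) at N = 20, against +6.6 and +3.9 at N = 40. With c = 12/21 it is +10.5 and +6.3 at N = 40, against +8.6 and +5.2 at N = 49.

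**5. Averaged over extended and non-extended outcomes.** If the weekly cohort ends at 20 when not extended, triggers of 6/15 to 8/15 and true rates of 40% to 60% give an overall bias of about −0.4 to −2.0 points, which is slightly downward.

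**6. Between schedules.** With both triggers at the observed counts, the weekly excess minus the single-dose excess (N = 49) is 6.65 − 8.60 = −1.95 points at 40% and 3.93 − 5.17 = −1.24 at 50%.

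**7. Patients enrolled after the look.** Their rate has no bias from this selection (simulation: within 0.01 points of the true rate).

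**The case against.** The strongest reply is that no section says a lower count would have blocked either extension. Section 2.6 gives small numbers as a reason, and the benchmarks in the documents are lower than the observed rates: about 30% in section 2.4 and 40% in section 11.2. Triggers near those benchmarks give much smaller excesses. The largest figure, +8.6, also needs a true rate of 40%, at which 12/21 or better occurs only 8.5% of the time. This stands, so the size can be given only as a range.

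A reader might infer that adding patients created the bias, or that the claim of greater accuracy is false. The documents do not support that. The early patients would have been reported anyway, and step 4 shows that enlargement dilutes their influence. Nor is the procedure biased upward overall: step 5 shows a slight downward bias. The upward lean exists only given extension, but extension is what happened.

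A reader might also infer that the comparison of schedules is distorted by a similar amount. Both rates are shifted the same way, so for comparably strict triggers the shift largely cancels. Nothing here shows a bias in toxicity rates.

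The looks, counts and reasons are already disclosed, and the evaluation is descriptive. That lowers the stakes but does not remove the lean from the pooled rate. Some later data exist: section 2.5 reports 18/32. If the 21 are among those 32, the later patients gave 6/11 (55%) against 57%. That is reassuring but too few to settle the matter.

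Finally, eligibility was widened at the first enlargement, so later single-dose patients may differ in prognosis. This stands and must be shown beside any before-and-after comparison.

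**Conclusion.** The point holds in conditional form. Given that both cohorts were extended after encouraging looks with no stated rule, the pooled response rate leans upward under every trigger considered. For true rates of 40% to 50%, the lean ranges from +0.2 to +6.6 points for the weekly cohort at 40 patients, and from +0.4 to +8.6 points for the single-dose cohort at 49. The documents do not fix the trigger, so no single value within these ranges can be called the bias. At the top of the range the weekly excess is a little under one standard error.

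The figures assume that the decision depended on the response count alone, that there was a sharp threshold, and that the response rate was the same before and after the look. The last is doubtful for the single-dose cohort because of the eligibility change. Enlarging was not the fault. The gap is that nothing in the plan separates the patients who prompted each extension from those who can test it.

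**What to change.** In sections 11.1 and 11.3:

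- Keep the pooled response rate, and state that it follows a data-driven extension and how each extension was decided.
- Beside it, report response with exact 95% intervals separately for patients counted at the look (15 weekly; 21 single-dose) and those enrolled afterwards (the added 20 weekly; 49 − 21 = 28 single-dose), using one response definition throughout.
- Show the five weekly patients accrued but not counted at the look (20 − 15) on their own line.
- Judge on the later patients whether the early result held up.
- For the single-dose cohort, show salvage status and first-remission duration by stage, so that a change in case mix can be told apart from regression of an early high rate.

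The cost is two or three extra table rows for response and wider intervals for the later patients: 10/20 gives about 27% to 73%, against 34% to 66% for 20/40. No further patients or data are needed.
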